Persistent diarrhoea continues to be an important cause of childhood morbidity and mortality in the developing countries. Improved case management might prevent mortality and morbidity due to this childhood illness. This study proposes to evaluate the feasibility and efficacy of a dietary treatment algorithm (shown efficacious in the hospital setting) as a home based management of children with non-severe persistent diarrhoea. This is a randomised, controlled, home-based intervention study. After examining the eligibility criteria the patients will be randomised to either intervention group (dietary treatment algorithm) or control (standard management). Patients in the intervention group, in addition to dietary manipulation, will receive oral rehydration therapy and vitamin-mineral supplementation. The initial diet (diet A) contains rice powder, cow's milk, and vegetable oil, and calorie content of 68 kcal/100 g. The diet B (containing rice powder, vegetable oil, egg white and sugar and calorie content 68 kcal/100 g) will be offered if there is no improvement of diarrhoea on day 7. Diet B will also be fed for 7 days. The patients under control group will receive standard management which include oral rehydration therapy and his/her usual diet or as advised by hospital physician, and also they will receive vitamin and minerals. 320 children aged 5 months to 36 months will be included in the study. After completion of the study the success rate with diet A, diet B and overall will be calculated and will be compared with that of the control group. The weight gain or loss of the patients of intervention group will also be compared with that of the control group. The factors related to treatment failure will also be analysed. This treatment algorithm might help to establish a rationale and effective treatment of persistent diarrhoea at home.

KEY PERSONNEL (List names of all investigators including PI and their respective specialties)

Name	Professional Discipline/Specialty	Role in the Project
1. [name]	SMO Gr I/Gastroenterology	Principal Investigator
2. [name]	SMO Gr II/Paediatrics	Co-Investigator
3. [name]	Scientist/Epidemiology	Co-Investigator
4. [name]	Interim Director/Paediatrician	Co-investigator

DESCRIPTION OF THE RESEARCH PROJECT

Hypothesis to be tested:

Concisely list in order, in the space provided, the hypothesis to be tested and the Specific Aims of the proposed study. Provide the scientific basis of the hypothesis, critically examining the observations leading to the formulation of the hypothesis.

Non-severe persistent diarrhoea patients can be treated at home using a simple dietary treatment algorithm.

Specific Aims:

Describe the specific aims of the proposed study. State the specific parameters, biological functions/ rates/ processes that will be assessed by specific methods (TYPE WITHIN LIMITS).

To evaluate the feasibility and efficacy of a dietary treatment algorithm as home based management of children with non-severe persistent diarrhoea.

Background of the Project including Preliminary Observations

Describe the relevant background of the proposed study. Discuss the previous related works on the subject by citing specific references. Describe logically how the present hypothesis is supported by the relevant background observations including any preliminary results that may be available. Critically analyze available knowledge in the field of the proposed study and discuss the questions and gaps in the knowledge that need to be fulfilled to achieve the proposed goals. Provide scientific validity of the hypothesis on the basis of background information. If there is no sufficient information on the subject, indicate the need to develop new knowledge. Also include the **significance and rationale** of the proposed work by specifically discussing how these accomplishments will bring benefit to human health in relation to biomedical, social, and environmental perspectives. (DO NOT EXCEED 5 PAGES, USE CONTINUATION SHEETS).

Diarrhoea continues to be a major cause of childhood morbidity and mortality worldwide. Persistent diarrhoea (PD), defined as episodes lasting for 14 days or more (1), accounts for only about ten percent of all diarrhoeal episodes but is associated with 30% to 50% of all diarrhoea related deaths (2-4).

Two major clinical categories of persistent diarrhoea can be distinguished (5):

- mild persistent diarrhoea with several daily loose stools but normal hydration status and which leads to growth faltering, more severe malnutrition and sometimes death due to diarrhoeal or nondiarrhoeal illness.
- severe persistent diarrhoea with dehydration and high purging rates (>7ml/kg/hour or very frequently large watery stools).

The pathogenesis of persistent diarrhoea is multifactorial with a wide spectrum of functional disturbances. Suggested mechanisms include in isolation or the combination of persistence of entero pathogens, bacterial overgrowth, continued mucosal injury, delayed mucosal repair, and host susceptibility (6). Delayed repair of mucosal injury and host susceptibility are strongly influenced by malnutrition which frequently precedes and occurs as a result of persistent diarrhoea (7). This

self-perpetuating cycle can be broken only through appropriate nutritional rehabilitation. Depending upon the severity of the mucosal damage, changes occur in the digestive, secretory, absorptive and reabsorptive capacities of macro and micronutrients (8). One of the most important absorptive problem is energy malabsorption due to malabsorption of carbohydrate and fat (9). Lack of clear guidelines for effective therapy has contributed to widely practiced but ineffective regimes such as the routine administration of antibiotics and use of low-caloric density diets (6). In consideration of the functional disturbances of the small intestine, modified diets have been used for the hospital-based management of persistent diarrhoea according to a dietary algorithm at ICDDR,B and other centres in Bangladesh with good results/success (10,11). Ideally, these diets should be inexpensive, culturally acceptable, locally available and provide adequate calories. Recent data have indicated that cereal/legume based diets with oil can be successful in treating children with persistent diarrhoea (12,13).

The addition of milk products can enhance the protein quality and micronutrients content of these diets, although the amount of lactose which can be tolerated by these children is not precisely known. The use of a full milk diet (the equivalent of 6 g lactose/kg/day) has resulted in increased stool output in most children with persistent diarrhoea (14). Recent studies indicate that modest amounts of milk products can be tolerated as part of a mixed diet given to treat acute (15,16) and persistent diarrhoea (12). Although not all children improve on this therapy (12,13), dietary intolerance (continued diarrhoea and/or poor weight gain) has been considered to be the most common cause for failure of these diets, but little exists to indicate which component or components of the diet is not tolerated. Providing a less complex form of carbohydrate by substituting monosaccharide (glucose) or disaccharide (sucrose) for at least some of the starch of a milk cereal diet might result in more effective therapy (17). Data from earlier studies indicate that chicken and egg protein are often well tolerated in children with diarrhoea (13,18) and can be used to replace milk protein. Fewer practical options are available for altering the nature of the fat component of the diet other than substituting vegetable fat for animal fat (19,20).

The International Working Group on Persistent Diarrhoea sponsored by the World Health Organisation and the Applied Diarrhoeal Disease Research Project (ADDR) evaluated a dietary treatment algorithm for use in developing countries. The overall success rate of the treatment algorithm was 80% (21). However, because this study was hospital-based, the study population was based with more severe cases. Although the children that are hospitalized represent an important group of children with PD, a large number of mild and moderate PD cases present to hospitals and clinics with mild or no sign of dehydration but who do not require hospitalisation. Moreover, if hospitalised, these children are at great risk to develop hospital-acquired infection (22). Yet, if these children do not receive appropriate nutritional therapy their diarrhoea may persist or worsen and accelerating their malnutrition with ultimately poor outcome. About 74% of patients presenting with persistent diarrhoea to ICDDR,B hospital are discharged from outpatient dept. (34%) and short-stay ward (39%) without proper nutritional advice (Surveillance data, 1993 to 1995). If a caregiver could use a dietary algorithm containing a simple, locally available diet as a *home-based* approach for the management of persistent diarrhoea, a great many children with PD would be expected to benefit. In addition the potential risk of nosocomial infection associated with hospitalization would be eliminated and the cost of patient care would be markedly reduced. We therefore, propose to evaluate the feasibility and efficacy of a home-based dietary treatment algorithm for the management of non-severe cases of persistent diarrhoea.

Significance

If this study demonstrates the feasibility and efficacy of the home-based nutritional management of persistent diarrhoea in children, then a substantial number of admissions to the hospital will be avoided, thereby reducing health care costs. Further it would also avoid the excess morbidity and mortality due to hospital-acquired infections associated with hospital-based management of persistent diarrhoea patients. This approach will also help to formulate guidelines for the management of non-severe persistent diarrhoea as one of the components in the Integrated Management of Childhood Illness (IMCI).

Research Design and Methods

Describe in detail the methods and procedures that will be used to accomplish the objectives and specific aims of the project. Discuss the alternative methods that are available and justify the use of the method proposed in the study. Justify the scientific validity of the methodological approach (biomedical, social, or environmental) as an investigation tool to achieve the specific aims. Discuss the limitations and difficulties of the proposed procedures and sufficiently justify the use of them. Discuss the ethical issues related to biomedical and social research for employing special procedures, such as invasive procedures in sick children, use of isotopes or any other hazardous materials, or social questionnaires relating to individual privacy. Point out safety procedures to be observed for protection of individuals during any situations or materials that may be injurious to human health. The methodology section should be sufficiently descriptive to allow the reviewers to make valid and unambiguous assessment of the project. **(DO NOT EXCEED TEN PAGES, USE CONTINUATION SHEETS).**

Design: This is a randomized, controlled, home-based intervention study.

Patients selection: Children attending the out-patient department of ICDDR,B hospital will be considered for selection into the study.

Inclusion criteria:

- a) Age 5 months to 36 months
- b) Duration of diarrhoea > 14 days
- c) Dehydration status-some or nil according to WHO criteria
- d) Written informed consent obtained from parents or legal guardian
- e) Accessible distance (within 15 km radius from ICDDR,B)

Exclusion criteria:

- a) Signs of systemic illness or other severe illnesses requiring hospital-based care (sepsis, severe pneumonia, meningitis, severe hyponatraemia or hypokalaemia)
- b) Severe malnutrition - wt/age <60% with or without edema.
- c) Patients with severe dehydration
- d) Bloody diarrhoea

Observation period:

All patients attending the outpatient department of ICDDR,B from 8 a.m. to 2 p.m. with history of persistent diarrhoea will be screened for eligibility for this study following the inclusion and exclusion criteria. The children who are eligible will initially be observed for 4 hours. A detailed clinical history will be recorded, and physical examination including anthropometry will be done. Children with some dehydration will be rehydrated with WHO-ORS.

Stool microscopy (*Giardia*, *Cryptosporidia*, *E. histolytica*), Stool culture (vibrios, shigella, salmonella and campylobacter) and urine analysis will be done.

Randomization:

After examining the eligibility criteria and informed consent signed by one of the parents/legal guardian, the patients will be randomized to either intervention group (dietary treatment algorithm) or control (standard management). Two strata of randomization list will be prepared by using random table. One stratum will be used for randomization of patients 5 months to 18 months and other stratum 19-36 months. The randomization lists will be prepared and serially numbered in sealed envelopes will be supplied containing the name of the treatment group. The envelopes will be opened by one of the investigators only after a patient has been irrevocably assigned to the study.

Case management

Intervention group

Treatment algorithm:

We have chosen to adapt the WHO algorithm designed for hospitalized children. The components of the treatment algorithm are summarized in Fig. 1, (Adapted from ref. 21) During the observation period, the mothers or other caregivers of the children will be educated to prepare the diet (Table I) and will be advised to feed study Diet (A) containing milk and rice-cereal mixture initially for 7 days. House visits will be done on every alternate days for follow up. During follow-up on day-3, if any treatable stool pathogen was identified from specimen obtained on Day 1, antimicrobial therapy will be provided for administration at home. Any skin infection, mild respiratory tract infection or urinary tract infection will also be treated with antimicrobial orally at home. Patients with skin infection will be treated with cloxacillin 50 mg/kg/day in 4 divided doses. Mild respiratory tract infection will be treated with amoxicillin 100 mg/kg/day in 3 divided doses. Urinary tract infection will be treated according to the culture and sensitivity results. All requisite medicines will be provided to all study patients, and ingredients of diets will be supplied to the mothers of the patients of the intervention group only.

At home, care-givers will record on a diarrhoea diary the frequency of stool each 24 hours, the stool consistency and time of cessation of diarrhoea. (Definitions below). After 7 days if diarrhoea continues, caregivers will be trained to prepare Diet B and will be instructed to feed Diet B - a milk free diet containing rice-cereal, vegetable oil, egg albumin and glucose mixture. The second diet (B) will also be fed for 7 days. For partially breastfed children the diets will be offered to attain energy intake >75 kcal/kg/day and for non-breastfed child the energy intake will be 110 kcal/kg/day. In addition multivitamin drops and zinc acetate are standard therapy for PD patients and will be given routinely to all children from the beginning of the study and for the following three weeks (Table 2). The dosage of multivitamin syrup will be 1 ml twice daily and Zinc acetate 10 mg twice daily. Oral rehydration with standard WHO-ORS will continue to maintain hydration to replace ongoing liquid stool losses until cessation of diarrhoea. The number of ORS packets used will be recorded.

On day 7 after beginning of diet A, if the patients are found to have normal stool (soft or formed), they will continue diet A.

After 7 days of second dietary regime, if diarrhoea persists, the patients will be admitted to the inpatient department for further evaluation and management according to the standard hospital practice at ICDDR,B.

Control group

The patients under control group will receive standard management which is advised to take WHO-ORS at home for maintenance of hydration and to continue his/her usual diet or as advised by hospital physician.

Follow-up:

All patients will be followed-up by home visits on every alternate day up to day 15 and then every 2 weeks thereafter up to 4 weeks. The children will be examined thoroughly including anthropometry at every follow up. Study personnel will also monitor the preparation of diet at home. Samples of prepared diet will also be collected and stored in deep freezer for quality study (e.g. composition and calories).

Fig. 1

DIETARY TREATMENT ALGORITHM

[figure not shown]

Table 1. Composition of study diets

Diet A		Diet B	
Milk/Suji/Litre (>4 mo age group)		Full-Strength Rice Suji/L	
Whole milk powder	40 g	Rice powder	60 g
Rice powder	40 g	Egg white	100 g (four)
Sugar	25 g	Oil (Soya)	30 ml
Oil (Soya)	25 g	Glucose	35 g
Mag. Chloride	0.5 g	Kcl	01 g
Potassium chloride	01 g	Mag. Chloride	0.5 g
Calcium	02 g	Calcium	02 g
After cooked volume	1000 ml	After cooked volume	1000 ml
Energy	67kcal/100ml	Energy	70 kcal/100 ml
Protein	4.4 gm/100ml	Protein	1.88 g/100 ml
PER*	8%	PER	10%

Table 2. Composition of Multivitamin drop (Composition per 1 ml)

Vitamin A U.S.P.	5000 IU
Vitamin D B.P.	640 IU
Ascorbic Acid (C) B.P.	50 mg
Thiamine Hcl (B ₁)	1.6 mg
Riboflavin Sodium Phosphate (B ₂) B.P.	1.37 mg
Pyridoxine B.P. (B ₆) U.S.P.	1.0 mg
Nicotinamide B.P.	10.0 mg
D-Panthenol U.S.P.	5.0 mg
Folic acid	0.25 mg

Justification of selection of diet A in the beginning

Dietary treatment algorithm is a well recognised treatment schedule for the nutritional management of children suffering from persistent diarrhoea. In ICDDR hospital, this treatment algorithm is also being followed. Justification of using Diet A initially is that this diet is easy to prepare, culturally acceptable, less modified as compared to Diet B. and less expensive (1 L Diet A costs Tk. 18.00 vs. Tk. 26.00 for Diet B).

Study withdrawal

Patients will be considered withdrawn from the study if a) their parents withdraw informed consent, or b) needs hospital care.

Patients will be considered for hospital care for the following reasons:

a) appearance of signs of some dehydration b) signs of severe infections (e.g. fever, cough, respiratory distress, tachycardia, tachypnoea, reluctant to feeding etc. c) signs of electrolyte imbalance (e.g. less responsive to environments or irritability, abdominal distensions etc.). After hospitalisation, the patients will be managed according to the standard hospital practice. Patients will be followed up even after withdrawn from the study. Data obtained from the withdrawn patients will also be included in the analysis upto the time of withdrawal.

Sample size

Sample size was calculated on the basis of two major outcome variables:

- a) success rate of diet therapy
- b) Growth faltering (percentage of patients experiencing weight loss during the study periods).

Based on the study (21) the sample size of this study is determined to be of 137 in each group on anticipated success rate (combining success of Diet A and Diet B) of 80% in the intervention group against an arbitrary standard success rate of 65% in the control group, considering a significance level of 5% and power of 80%. Assuming a dropout of 15%, a total sample of 320 patients was calculated.

We are not expecting significant difference in recovery rate on diet A and the control. However, if the difference is 20% or more, then the present sample size will be enough to detect the significant difference.

Thirty percent of children under control group is anticipated to experience weight loss as opposed to 10% in the intervention group during the study periods. Considering a significance level of 5% and 80% power, the sample size in each group is calculated as 60.

Finally, we consider the total sample size for this study as 320.

Organization of the trial

Patients attending in the treatment centre of ICDDR,B will be evaluated for recruitment for study.

Study Schedule

The study will be started after the approval of RRC and ERC and allocation of budget. The first two months will be utilized for staff recruitment, training and pretrial. 20 months will be needed for patients study. Last 2 months will be utilized for data analysis and reporting of the study results.

Definition

Diarrhoea: Three or more abnormal stools (loose or watery) during a 24-hour period.

Stool consistency: Abnormal stool - loose/watery or abnormal as considered by mother.
Normal stool - soft/formed or normal as considered by mother.

Cessation of diarrhoea: Last abnormal stool followed by normal stool at least for three days.

Success of diet therapy: Cessation of diarrhoea within 7 days of starting of the modified diet (diet A or diet B).

Facilities Available

Describe the availability of physical facilities at the place where the study will be carried out. For clinical and laboratory-based studies, indicate the provision of hospital and other types of patient's care facilities and adequate laboratory support. Point out the laboratory facilities and major equipments that will be required for the study. For field studies, describe the field area including its size, population, and means of communications. (TYPE WITHIN THE PROVIDED SPACE).

ICDDR,B treatment centre will be used for patients recruitment, observation, and training of the caregivers of the patients.

Data Analysis

Describe plans for data analysis. Indicate whether data will be analyzed by the investigators themselves or by other professionals. Specify what statistical softwares packages will be used and if the study is blinded, when the code will be opened. For clinical trials, indicate if interim data analysis will be required to monitor further progress of the study. (TYPE WITHIN THE PROVIDED SPACE).

Statistical analysis

Statistical analysis will be done using SPSS/PC software. Percentage of success of treatment for each dietary intervention and overall success rate will be calculated. Relative risk ratios and their associated 95% confidence intervals will be calculated to identify variables (e.g. inappropriately making and feeding the diet, associated other infections, education of mothers, family income, no. of children in the family, source of drinking water, antibiotic use before admission, type of dehydration before intervention, frequency of stool etc.) that were related to the treatment failure. Overall success rate (the number of patients recovered at the end of 10 days) in the intervention group will be compared with that of control group. The number of patients lost weight will also be compared between the groups.

Adjusted analysis will be done by constructing life tables of the two groups and will be compared by log rank test.

Ethical Assurance for Protection of Human Rights

Describe in the space provided the justifications for conducting this research in human subjects. If the study needs observations on sick individuals, provide sufficient reasons for using them. Indicate how subject's rights are protected and if there is any benefit or risk to each subject of the study.

This intervention study will be conducted among the children under 5 years of age because these children are the sufferers from this illness of persistent diarrhoea. Written informed consent will be duly signed by the parents or legal guardians.

There is no risk for this intervention on the other hand they might be benefited from this intervention.

Use of Animals

Describe in the space provided the type and species of animal that will be used in the study. Justify with reasons the use of particular animal species in the experiment and the compliance of the animal ethical guidelines for conducting the proposed procedures.

Not applicable.

Literature Cited

Identify all cited references to published literature in the text by number in parentheses. List all cited references sequentially as they appear in the text. For unpublished references, provide complete information in the text and do not include them in the list of Literature Cited. There is no page limit for this section, however exercise judgment in assessing the "standard" length.

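### The Project Summary plans to compare Diet B success with the control group, but Diet B reaches only Diet A non-responders; the comparison is not randomised, is tilted against Diet B, and is absent from the Statistical analysis section

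*Protocol*

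**What the plan says.** The Project Summary announces three comparisons with control: the "success rate with diet A, diet B and overall will be calculated and will be compared with that of the control group".

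The rest of the protocol determines what a Diet B rate can be:

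- **Randomisation.** Children are allocated to the algorithm as a whole or to standard management: "the patients will be randomized to either intervention group (dietary treatment algorithm) or control (standard management"). Nobody is randomised to Diet B.
- **Who receives Diet B.** The Summary says that Diet B "will be offered if there is no improvement of diarrhoea on day 7". Case management, Intervention group, says: "After 7 days if diarrhoea continues, caregivers will be trained to prepare Diet B". Responders stay where they are: "if the patients are found to have normal stool (soft or formed), they will continue diet A".
- **How success is counted.** The Definition section has "Success of diet therapy: Cessation of diarrhoea within 7 days of starting of the modified diet (diet A or diet B"). The clock restarts with each diet. No corresponding start, window or denominator is given for controls.

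The Statistical analysis section differs from the Summary. For the single diets it says only: "Percentage of success of treatment for each dietary intervention and overall success rate will be calculated". Its stated between-group comparisons are overall success (at 10 days), the number of children who lost weight, and a log-rank comparison of the two groups' life tables.

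**The concern.** The only children who can enter a Diet B success rate are those who did not recover on Diet A. They are a subset formed after randomisation by non-response, and their 7-day window opens about a week after entry. No matching control subset is defined, so read plainly the reference is the control group as a whole. That group includes the children who recover easily. The two rates then differ in who is counted and in when counting starts, and neither difference is protected by the randomisation.

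The direction is predictable: removing the early responders lowers the Diet B rate relative to an unselected group. At stake is the reading of the algorithm's second step. The same data could show the algorithm beating standard management and Diet B doing worse than standard management, with the second result arising only from selection. The protocol hopes to inform guidelines for non-severe persistent diarrhoea (Significance), so a misleading statement about Diet B would matter.

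**Working it through.** **Inputs from the protocol (Sample size).** Anticipated success is 80% in the intervention group (Diets A and B combined) and 65% in the control group; 5% significance, 80% power; 137 per group; 15% dropout; 320 in total. The text after the calculation expects no significant difference between Diet A and control, but gives no Diet A rate.

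**Reproducing the plan's own figure.** For two proportions with a two-sided test, pooled variance under the null and no continuity correction, the mean proportion is 0.725 and

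n = [1.96·√(2·0.725·0.275) + 0.842·√(0.80·0.20 + 0.65·0.35)]² / 0.15² = 137.9,

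that is 138 per group against the stated 137. Dropout: 274/0.85 = 322, against the stated 320. Both are reproduced closely enough.

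**Implied Diet B rate.** Let a be success on Diet A and b be success on Diet B among those who start it. If every Diet A failure goes on to Diet B,

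overall = a + (1 − a)·b, so b = (0.80 − a)/(1 − a).

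The number starting Diet B is 137·(1 − a). Each b is compared with 65% of 137 controls by the pooled two-proportion z test, two-sided:

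| Assumed Diet A rate | Number starting Diet B | Implied Diet B rate | Difference from 65% | z | p |
|---|---|---|---|---|---|
| 40% | 82 | 66.7% | +2 points | 0.25 | 0.80 |
| 50% | 68.5 | 60.0% | −5 | −0.70 | 0.48 |
| 55% | 62 | 55.6% | −9 | −1.27 | 0.20 |
| 60% | 55 | 50.0% | −15 | −1.92 | 0.055 |
| 65% | 48 | 42.9% | −22 | −2.69 | 0.007 |
| 70% | 41 | 33.3% | −32 | −3.60 | <0.001 |

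Example at a = 65%: b = 0.15/0.35 = 0.429, about 21 successes among 48 starters. The pooled proportion is 0.593, the standard error 0.082, and z = (0.429 − 0.65)/0.082 = −2.69. If these rates were true, the chance of a significant result against Diet B would be about 77%.

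**Where the sign changes.** Setting b = 0.65 gives a = (0.80 − 0.65)/(1 − 0.65) = 42.9%. Above that Diet A rate, Diet B shows a deficit although the algorithm is assumed 15 points better.

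**If the algorithm had no effect.** With 65% overall and a = 50%, b = 0.15/0.50 = 30%. That is an apparent deficit of 35 points when the arms do not differ.

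**A closer reference.** Suppose control recovery is 65% by day 14 and 40%, 50% or 60% by day 7 (assumed). Recovery over days 8–14 among controls still ill at day 7 is then 0.25/0.60 = 41.7%, 0.15/0.50 = 30.0% or 0.05/0.40 = 12.5%. Against these, a Diet B rate of 42.9% no longer looks poor. This contrast is not randomised either, but it shows how far the choice of reference drives the impression.

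**The case against.** The strongest defence is that the comparison appears in one sentence of the Summary. The Statistical analysis section calculates a rate for each diet and compares only overall success, weight loss and the life tables between groups. The hypothesis and aim concern the algorithm, and the main sample size rests on combined success. Outside the Summary, the only single-diet contrast with control is the remark on Diet A after the sample size calculation. This stands. It limits the weight of the point, but it also confirms that the two sections disagree, and the protocol does not say which governs.

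A second defence is that the Summary promises a comparison and not a significance test, and that the control window and denominator are nowhere stated. This also stands. Taking all controls from entry is the plain reading, but it remains an inference. A 7-day control rate would be lower and the gap smaller; the selection of non-responders would remain.

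Third, a reader might infer that the trial would find Diet B significantly worse than standard management. The protocol does not support that as a general statement. It gives no Diet A rate. The 65% control rate was set against success on both diets combined and may not be a 7-day rate, so a 7-day Diet A rate similar to control could be well below 65%. At an assumed 60% the result just misses the 5% level, at 50% it is far from it, and below 42.9% there is no deficit.

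A reader might also infer that the main result is compromised. It is not compromised by this comparison: the overall contrast is between randomised arms.

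**Conclusion.** The point holds in a limited form and should be fixed. As worded in the Summary, Diet B versus control compares children selected for non-response, on a later clock, with a group not so selected. It is not protected by randomisation and is biased against Diet B. The Summary and the Statistical analysis section also disagree on whether it will be made.

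Under the planning rates, the apparent difference runs from 2 points in favour of Diet B (Diet A at 40%) to 32 points against it (Diet A at 70%). It becomes significant at 5% only for Diet A rates above about 60%. These figures assume 137 per group, that every Diet A failure starts Diet B, and a 65% control rate taken over all controls. The protocol fixes neither the Diet A rate nor the control window, so the whole range should be shown and no single value treated as the expected result.

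**What to change.** 1. Delete the Diet B versus control comparison from the Project Summary so that it agrees with the Statistical analysis section.
2. Report Diet B success as a description among the children who started it, with that denominator stated.
3. Limit between-group tests to whole randomised arms at the same time from randomisation: overall success and, if it is kept, Diet A versus control at day 7.
4. Reconcile the time point for overall success. The Statistical analysis section says 10 days, whereas Diet B starts after day 7 and runs to day 14, so a 10-day count misses most of the Diet B window.
5. If a control figure for days 8–14 is shown beside Diet B, restrict it to controls still ill at day 7 and label it non-randomised and exploratory.

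Items 3 and 5 need stool status for controls at fixed days. The stool diary is described only under the intervention group. Follow-up promises alternate-day home visits to day 15 for all patients, with examination and anthropometry, but does not mention stool records. The protocol should state that stool status is recorded for controls at those visits.

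Otherwise the change is to wording. One invalid comparison is lost. The randomised overall comparison and the sample size stay as they are: 80% versus 65% still has 79.7% power at 137 per group and 85.5% at 160.
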